1.0 TRIAL SUMMARY

Abbreviated Title	Pembrolizumab and palliative radiotherapy in metastatic gastroesophageal cancer
Trial Phase	II
Clinical Indication	SCC and/or adenocarcinoma of the esophagus, GEJ, and stomach
Trial Type	Prospective; Biomarker analysis
Route of administration	Intravenous
Trial Blinding	None
Treatment Groups	All patients will be assigned to the same therapy of palliative radiotherapy of 30 Gy over 10 fractions for symptoms from their primary tumor or a single target metastatic site in combination with pembrolizumab at a fixed dose of 200 mg every 3 weeks.
Number of trial subjects	14
Estimated enrollment period	24 months
Estimated duration of trial	36 months from the first patient signing informed consent until the last patient's last visit.
Duration of Participation	Patients will complete radiation therapy of 30 Gy in 10 fractions and will continue pembrolizumab until confirmed disease progression, or intolerable toxicity, or an initial 35 administrations (approximately 2 years). Patients who stop pembrolizumab with stable disease or better or 35 administrations of therapy without progression may be eligible at the discretion of the investigator to receive up to an additional year of pembrolizumab therapy. Patients with evidence of progressive disease (PD) on imaging and are clinically stable may continue to be treated at the discretion of the investigator.

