2.0 TRIAL DESIGN

2.1 Trial Design

This is a single-arm, prospective, phase II, biomarker analysis trial of pembrolizumab in combination with palliative radiotherapy for patients with metastatic squamous cell or adenocarcinoma of the esophagus, stomach, or gastroesophageal junction (GEJ). We will enroll 14 patients within our institution who are in need of palliative radiation for symptoms related to their primary tumor including pain, dysphagia, and bleeding. Patients with a single metastatic site in need of palliative radiation (e.g., pain from a bony metastasis, enlarged lymph nodes, liver metastasis, etc.) will also be eligible provided they have other measurable metastatic sites outside of the radiation field. The exception will be patients who require palliative radiation to a symptomatic central nervous system (CNS) metastasis. The first dose of palliative radiation and first dose of pembrolizumab will commence on cycle 1, day 1.

Participation in this trial will be dependent on patients having a metastatic site amenable to ultrasound and/or CT-guided biopsy, inclusive of patients with malignant ascites amenable to ultrasound-guided aspiration, and agreeing to provide pre- and post-treatment biopsies for the

IRB Protocol No. 16099

Version: 04

[figure not shown]
Version Date: 10/16/2019

biomarker analysis primary endpoint of the study. Patients who are undergoing palliative radiation for a single target metastatic site, and only the primary tumor is amenable to biopsy are also eligible to participate if they consent to endoscopic pre- and post-treatment biopsies.

Treatment will continue until documented clinical PD, unacceptable AE(s), intercurrent illness that prevents further administration of treatment, investigator's decision to withdraw the patient, patient withdraws consent, pregnancy of the subject, noncompliance with trial treatment or procedure requirements, completion of 35 administrations (approximately 2 years) of treatment with study medication or achievement of a complete response.

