9.2 Secondary Objectives

Secondary objectives such as ORR per RECIST 1.1 and irRECIST, PFS, and OS are exploratory, though will also be documented, along with toxicity. All patients who receive at least one dose of pembrolizumab will be included in the safety analysis. Stool/oral microbiomic profiling and germline miRNA biomarker panel analyses will also be correlated with secondary outcome measures of ORR and toxicities.

While overlapping toxicities are not anticipated with the combination of pembrolizumab and RT, the initial treatment of patients within this trial warrants a careful review of toxicity:

- **Toxicity-based Interim Analysis:** A study hold will be placed for re-evaluation at the proposed starting dose as accrual proceeds on this phase II study according to the following rule: The study will hold pending an amendment if 3 patients discontinue therapy after cycle 1 due to treatment-related toxicity. This rule has a 97% chance of holding the study if the true discontinuation rate due to toxicity on cycle 1 is 50%. It has a 15% chance of holding if the true discontinuation rate on cycle 1 is 15%.
- **Treatment-related mortality stopping rule:** Any treatment-related death will hold the study accrual pending review by the PI, Sponsor, and DSMB/IRB.

With 14 patients, there is 96% power to detect at least one responder if the true response rate is 21% or higher, which is in the range of 22% in the phase I trial of pembrolizumab among gastric cancer patients with PD-L1 overexpression. As a result, failure to observe any response in the 14 patients would result in lack of enthusiasm for the combination of pembrolizumab and RT in this patient population. PFS and OS will be determined using the Kaplan-Meier method.

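### The toxicity hold rule in section 9.2 (3 patients) does not have its stated 97% and 15% hold probabilities; with 14 patients they are 99% and 35%.

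*Combined protocol and SAP*

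**What the plan says.** Under the toxicity-based interim analysis, section 9.2 states: "The study will hold pending an amendment if 3 patients discontinue therapy after cycle 1 due to treatment-related toxicity". The rule is applied "as accrual proceeds on this phase II study according to the following rule", so it runs continuously during enrolment. No look schedule and no other denominator is given.

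Two operating characteristics follow:

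- At the unacceptable rate: "This rule has a 97% chance of holding the study if the true discontinuation rate due to toxicity on cycle 1 is 50"%.
- At the acceptable rate: "It has a 15% chance of holding if the true discontinuation rate on cycle 1 is 15"%.

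The sample size is the same throughout. Section 2.1 says "We will enroll 14 patients within our institution", the summary table in section 1.0 says "Number of trial subjects 14", and the power calculation in section 9.1 uses the same number.

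**The concern.** A trigger of 3 among 14 patients is low when the true rate is 15%. The expected number of events is then 14 × 0.15 = 2.1, so reaching 3 is not unusual, and a stated hold probability of only 15% looks too small.

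This is the only toxicity rule in the plan with stated operating characteristics, and those who approve and monitor the trial rely on them. A hold is costly: the study stops until the protocol is amended, and section 12.1 requires IRB approval of an amendment before it is implemented. If the stated figures belong to a different trigger, the plan also leaves open what happens when the third patient discontinues. The text requires a hold, but the rule that matches the probabilities does not.

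**Working it through.** **Inputs**

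- n = 14 patients (sections 1.0, 2.1 and 9.1).
- Trigger r = 3 discontinuations for treatment-related toxicity, read as X ≥ 3 (section 9.2).
- True rates p = 0.50 and p = 0.15, with stated hold probabilities of 97% and 15% (section 9.2).

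**Method.** Let X be the number of toxicity discontinuations, binomial(n, p). With one fixed trigger and continuous monitoring, the study holds at some point exactly when the final count would reach r. Hence P(hold) = P(X ≥ r) = 1 − Σ C(n,k) p^k (1−p)^(n−k), summed over k = 0 to r−1.

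**Rule as written, 3 of 14**

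- p = 0.50: 1 − (1 + 14 + 91)/2^14 = 1 − 106/16384 = 0.9935. Stated: 0.97.
- p = 0.15: the terms for k = 0, 1 and 2 are 0.1028, 0.2539 and 0.2912, which sum to 0.6479. So P(hold) = 0.3521. Stated: 0.15.

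Neither stated figure is reproduced. The gap is 2.4 percentage points at the 50% rate and 20 points at the 15% rate (0.3521/0.15 = 2.35 times the stated value).

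**Trigger of 4 of 14**

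- p = 0.50: 1 − (106 + 364)/16384 = 1 − 470/16384 = 0.9713.
- p = 0.15: adding the k = 3 term, 0.2056, brings the sum to 0.8535. So P(hold) = 0.1465.

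These round to the stated 97% and 15%.

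**Other readings**

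| Reading | p = 0.50 | p = 0.15 |
|---|---|---|
| Stated in section 9.2 | 97% | 15% |
| 3 of 14 (as written) | 99.4% | 35.2% |
| 3 of 13 (a hold must still stop an enrolment) | 98.9% | 30.8% |
| 3 of 11 | 96.7% | 22.1% |
| 3 of 10 | 94.5% | 18.0% |
| 3 of 9 | 91.0% | 14.1% |
| 4 of 14 | 97.1% | 14.7% |

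A smaller denominator with a trigger of 3 can approach one of the stated figures but not both. In a search over every n from 3 to 30 and every trigger, 4 of 14 was the only single-threshold rule within 2 points of both. Some two-look rules (3 events within the first 3 to 7 patients, then 4 of 14) give about 97% and 15% to 17%. The protocol describes no such looks, and these rules also end with a trigger of 4.

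**Sensitivity to the true rate.** With a trigger of 3 of 14, P(hold) is 15.8% at p = 0.10 and 55.2% at p = 0.20. With a trigger of 4 of 14 it is 4.4% and 30.2%.

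**The case against.** The strongest reply is that the error is on the safe side. Holding at 3 is a clear instruction. It stops the study more often than the stated probabilities imply, and detection at the 50% rate is slightly better than claimed. The consequence is a pause for re-evaluation, not termination. Other safeguards exist: the hold for any treatment-related death (section 9.2), the early-termination criteria (section 5.7) and team monitoring with reports to the committee (section 8.2). The primary biomarker analysis does not use these figures. All of this is correct, and it limits the harm to unneeded holds as long as the team follows the text. It does not make the stated 15% true.

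Three narrower points also deserve an answer.

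- **A third event in the last patient leaves no accrual to hold.** On that reading the figure is 30.8%, still about twice the stated value.
- **The event window is loose.** The trigger counts discontinuations after cycle 1, while the probabilities refer to the rate on cycle 1. The calculation treats these as the same event. If later discontinuations also count, the hold probability at a 15% cycle-1 rate can only rise, so the gap widens.
- **That 4 of 14 was the rule calculated is an inference.** The documents show no calculation. The match at the trial's own sample size is close, but it does not show which rule was intended.

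**Conclusion.** The concern holds. The rule as written has hold probabilities of 99.4% at a 50% rate and 35.2% at a 15% rate, not 97% and 15%. At the rate the plan treats as acceptable, a hold occurs in roughly one trial in three, where the plan implies about one in seven. The discrepancy at the 50% rate is small and has little practical effect.

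The result assumes 14 patients who can all contribute an event, independent outcomes with a common rate, and a trigger met at 3 or more. Limiting the rule to the first 13 patients gives 31%, and the conclusion is unchanged.

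Patients would be less protected than the text promises only if the team acted on a trigger of 4. The hold would then wait for one more discontinuing patient. Ignoring the cap at 14, that is on average 1/0.50 = 2 further enrolments at a 50% rate and 1/0.15 ≈ 6.7 at a 15% rate.

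**What to change.** Make the trigger and the two probabilities in section 9.2 agree.

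- If the trigger of 3 stays, restate the hold probabilities as 99% and 35%.
- If 97% and 15% are the properties that were reviewed and wanted, the sponsor and the monitoring committee should confirm whether 4 of 14 was the intended trigger and correct the text.

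The documents do not show which was meant, so no trigger is recommended here. The same edit should say whether only cycle-1 discontinuations count, because the restated probabilities depend on it.

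The cost is a short edit to section 9.2, with no added patients or procedures. If 3 is kept, the plan has to show a less favourable chance of an unneeded hold.

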10.0 LABELING, PACKAGING, STORAGE AND RETURN OF CLINICAL SUPPLIES

10.1 Investigational Product

The investigator shall take responsibility for and shall take all steps to maintain appropriate records and ensure appropriate supply, storage, handling, distribution and usage of investigational product in accordance with the protocol and any applicable laws and regulations.

Clinical Supplies will be provided by Merck as summarized in [Table 7](#).

Table 7 Product Descriptions

Product Name & Potency	Dosage Form
Pembrolizumab 50 mg	Lyophilized Powder for Injection
Pembrolizumab 100 mg/ 4mL	Solution for Injection

10.2 Packaging and Labeling Information

Clinical supplies will be affixed with a clinical label in accordance with regulatory requirements.

10.3 Clinical Supplies Disclosure

This trial is open-label; therefore, the subject, the trial site personnel, the Sponsor and/or designee are not blinded to treatment. Drug identity (name, strength) is included in the label text; random code/disclosure envelopes or lists are not provided.

10.4 Storage and Handling Requirements

Clinical supplies must be stored in a secure, limited-access location under the storage conditions specified on the label.

Receipt and dispensing of trial medication must be recorded by an authorized person at the trial site.

Clinical supplies may not be used for any purpose other than that stated in the protocol.

10.5 Returns and Reconciliation

The investigator is responsible for keeping accurate records of the clinical supplies received from Merck or designee, the amount dispensed to subjects, and the amount remaining at the conclusion of the trial.

Upon completion or termination of the study, all unused and/or partially used investigational product will be destroyed at the site per institutional policy. It is the Investigator's responsibility to arrange for disposal of all empty containers, provided that procedures for proper disposal have been established according to applicable federal, state, local and institutional guidelines and procedures, and provided that appropriate records of disposal are kept.

11.0 DATA REPORTING

11.1 Data Reporting

11.1.1 Confidentiality and Storage of Records

The original data collection forms will be sent to the CTO and stored in a locked area. This protocol uses Electronic Data Collection per institutional policy for investigator-initiated trials, and the data will be stored in encrypted, password protected, secure computers that meet all HIPAA requirements. When results of this study are reported in medical journals or at meetings, identification of those taking part will not be disclosed. Medical records of subjects will be securely maintained in the strictest confidence, according to current legal requirements. They will be made available for review, as required by the FDA, HHS, or other authorized users such as the NCI, under the guidelines established by the Federal Privacy Act and rules for the protection of human subjects.

11.1.2 Subject Consent Form

At the time of registration, the original signed and dated Informed Consent form, HIPAA research authorization form, and the California Experimental Subject's Bill of Rights (for the medical record) and three copies (for the subject, the research record, and the Coordinating Center) must be available. All Institutional, NCI, Federal, and State of California requirements will be fulfilled.

11.1.3 Data Collection Forms and Submission Schedule

All data will be collected 2 weeks prior using MediData Rave. Data will be sent to the location identified in Section 11.1.1 and stored in a secure location.

11.1.3.1 Eligibility Checklist

The Eligibility Checklist must be completed by a protocol nurse or clinical research associate and signed by an authorized investigator prior to registering the subject.

11.1.3.2 Prior Therapy Forms and On-Study Forms

Within 2 weeks of registration, the clinical research associate will submit data in regards to prior therapies the patient has received, if applicable.

12.0 HUMAN SUBJECT ISSUES

12.1 Institutional Review Board

In accordance with City of Hope policies, an Institutional Review Board (IRB) that complies with the federal regulations at 45 CFR 46 and 21 CFR 50, 56 and State of California Health and Safety code, Title 17, must review and approve this protocol and the informed consent form prior to initiation of the study. All institutional, NCI, Federal, and State of California regulations must be fulfilled.

Any documents that the IRB may need to fulfill its responsibilities (such as protocol, protocol amendments, Investigator's Brochure, consent forms, information concerning patient recruitment, payment or compensation procedures, or other pertinent information) will be submitted to the IRB. The IRB's written unconditional approval of the study protocol and the informed consent document will be in the possession of the investigator before the study is initiated.

The IRB will be informed of revisions to other documents originally submitted for review; serious unexpected or unanticipated adverse experiences occurring during the study, and any additional adverse experiences in accordance with the standard operating procedures and policies of the IRB; new information that may affect adversely the safety of the patients of the conduct of the study; an annual update and/or request for re-approval; and when the study has been completed.

Any amendment to the protocol document and accompanying informed consent document/template, as developed and provided by the PI, will require review and approval by the COH IRB before the changes are implemented in the study.

12.2 Recruitment of Subjects

The Gastrointestinal Medical Oncology Division will identify patients undergoing treatment for metastatic gastroesophageal cancer at City of Hope.

12.3 Study location and Performance Sites

This study will be performed at COH.

12.4 Confidentiality

Participant confidentiality is strictly held in trust by the investigators, study staff, and the sponsor(s) and their agents. This confidentiality is extended to cover testing of biological samples in addition to any study information relating to participants.

This research will be conducted in compliance with federal and state requirements relating to protected health information (PHI), including the requirements of the Health Insurance Portability and Accountability Act of 1996 (HIPAA). HIPAA regulations require a signed participant authorization informing the participant of the nature of the PHI to be collected, who will have access to that information and why, who will use or disclose that information, and the

rights of a research participant to revoke their authorization for use of their PHI. In the event that a participant revokes authorization to collect or use PHI, the investigator, by regulation, retains the ability to use all information collected prior to the revocation of participant authorization. For participants that have revoked authorization to collect or use PHI, attempts should be made to obtain permission to collect at least vital status (i.e. that the participant is alive) at the end of their scheduled study period.

Release of research results should preserve the privacy of medical information and must be carried out in accordance with Department of Health and Human Services Standards for Privacy of Individually Identifiable Health Information, 45 CFR 164.508. When results of this study are reported in medical journals or at meetings, identification of those taking part will not be disclosed and no identifiers will be used.

Medical records of participants will be securely maintained in the strictest confidence, according to current legal requirements. Data will be entered, analyzed and stored in encrypted, password protected, secure computers that meet all HIPAA requirements. All data capture records, drug accountability records, study reports and communications will identify the patient by initials and the assigned patient number. Source documents provided to coordinating center for the purpose of auditing or monitoring will be de-identified and labeled with the study number, participant ID, and participant initials.

The investigator/institution will permit direct access to source data and documents by sponsor representatives, the FDA, and other applicable regulatory authorities. The access may consist of trial-related monitoring/ auditing, IRB reviews, and FDA/regulatory authority inspections. The participant's confidentiality will be maintained and will not be made publicly available to the extent permitted by the applicable laws and regulations.

12.5 Financial Obligations and Compensation

The investigational drug, pembrolizumab, will be provided free of charge by City of Hope and Merck. Should this drug or device become commercially available during the course of treatment, the research participant and/or the insurance carrier may be asked to pay for the costs of the drug.

The standard of care drug(s) and procedures provided will be the responsibility of the research participant and/or the insurance carrier. The research participant will be responsible for all copayments, deductibles, and other costs of treatment and diagnostic procedures as set forth by the insurance carrier. The research participant and/or the insurance carrier will be billed for the costs of treatment and diagnostic procedures in the same way as if the research participant were not in a research study. However, neither the research participant nor the insurance carrier will be responsible for the research procedures related to this study.

In the event of physical injury to a research participant, resulting from research procedures, appropriate medical treatment will be available at the City of Hope to the injured research participant, however, financial compensation will not be available.

The research participant will not be paid for taking part in this study.

12.6 Informed Consent Processes

The Principal Investigator or IRB approved named designate will explain the nature, duration, purpose of the study, potential risks, alternatives and potential benefits, and all other information contained in the informed consent document. In addition, they will review the experimental subject's bill of rights and the HIPAA research authorization form. Prospective participants will be informed that they may withdraw from the study at any time and for any reason without prejudice, including as applicable, their current or future care or employment at City of Hope or any relationship they have with City of Hope. Prospective participants will be afforded sufficient time to consider whether or not to participate in the research.

After the study has been fully explained, written informed consent will be obtained from either the prospective participant or his/her guardian or legal representative before study participation. The method of obtaining and documenting the informed consent and the contents of the consent must comply with the ICH-GCP and all applicable regulatory requirements.

Before implementing any study procedure, informed consent shall be documented by the use of a written consent form approved by the IRB and signed and dated by the prospective participant or his/her legally authorized representative at the time of consent. A copy of the signed informed consent will be given to the participant or his/her legally authorized representative. The original signed consent must be maintained by the investigator and available for inspection sponsor designated representatives, or regulatory authority at any time. Informed consent is a process that is initiated prior to the individual agreeing to participate in the study and continues throughout study participation.

REFERENCES

